 State of Illinois Department or Agency, please specify :  Other, please specify :
4C. Sponsor-assigned grant number, if known:
4D. A complete copy of the funding proposal or contract is attached.  Attached, please specify title : Membership Agreement for Artificial Intelligence Accessibility Coalition
4E. Funding Agency Official To Be Notified of IRB Approval (if Applicable) Name: Agency: E-mail: Phone:

Section 5. CONFLICTS OF INTEREST

Please indicate below whether any investigators or members of their immediate families have any of the following. If the answer to any of the following items is yes, please submit the University of Illinois approved conflict management plan. If you have any questions about conflicts of interest, contact [contact].

5A. Financial interest or fiduciary relationship with the research sponsor (e.g. investigator is a consultant for the research sponsor).  Yes  No
5B. Financial interest or fiduciary relationship that is related to the research (e.g. investigator owns a startup company, and the intellectual property developed in this protocol may be useful to the company).  Yes  No
5C. Two or more members of the same family are acting as research team members on this protocol.  Yes  No

Section 6. SUMMARY & PURPOSE OF RESEARCH

6A. In lay language, briefly summarize the objective and significance of the research.

The goal of the Speech Accessibility Project at the UIUC Beckman Institute (<https://speechaccessibilityproject.beckman.illinois.edu>) is to collect, annotate, and curate a shared database of speech samples from people with atypical speech, and share this data set with researchers at other organizations. This two-year project plans to collect 1,200,000 speech samples from 2,000 people, each of whom will provide 600 samples. In Year 1, the initial focus will be people with Parkinson's. In Year 2, four more etiologies of interest will be recruited (such as ALS patients, stroke patients, etc.). UIUC will build an open-source software infrastructure to collect annotated speech samples and share these data in an appropriately secure fashion with researchers from our partner technology companies (and eventually, other organizations as well) so that they can use these data to improve their automatic speech recognition algorithms. This project promotes diversity, equity, and inclusion by helping technology companies to fully support all types of speech, and it is also more efficient and less burdensome for these specialized patient populations to have one centralized "collector" of speech samples.

**6B. Indicate if your research includes any of the following:**

- Secondary data (use of data collected for purposes other than the current research project)
- Data collected internationally (include [International Research Form](#))
- Translated documents (include [Certificate of Translation Form](#) and translated documents)
- Research activities will take place at Carle (include documentation (email or letter) from Carle stating that the review of your [Research Services Request Form](#) is complete)

6C. Letters of support from outside institutions or entities that are allowing recruitment, research, or record access at their site(s) are attached. Yes Not Applicable

Section 7. PROCEDURES

7A. Select all research methods and/or data sources that apply.

- Surveys or questionnaires, *select all that apply:* Paper Telephone Online
- Interviews
- Focus groups
- Field work or ethnography
- Standardized written, oral, or visual tests
- Taste or smell testing
- Intervention or experimental manipulation
- Exercise and muscular strength testing
- Noninvasive procedures to collect biological specimens (e.g., hair and nail clippings, saliva, etc.)
- Noninvasive procedures to collect physiological data (e.g., physical sensors, electrocardiography, etc.)
- Procedures involving radiation
- Recording audio and/or video and/or taking photographs: Yes
- Recording other imaging
- Materials that have already been collected or already exist, *specify source of data:*
- [HIPAA-protected data](#)
- [FERPA-protected data](#)
- [GDPR-protected data](#)
- Other, *please specify:*

7B. List all testing instruments, surveys, interview guides, etc. that will be used in this research.

Drafts or final copies of all research materials are attached. Yes

7C. List approximate study dates. February 2023 – August 2024**7D. What is the duration of participants' involvement?** Up to 5 hours, which is the time estimated to be trained on the system and then use it to provide 600 speech samples, where each sample is approximately 5 to 10 seconds of speech.**7E. How many times will participants engage in research activities?** Multiple times as needed at their own pace and convenience to record speech samples.**7F. Narratively describe the research procedures in the order in which they will be conducted.**

The goal of our project is to collect 1,200,000 speech samples from 2,000 people with dysarthria, where we expect to collect data from 400 people each from five different patient populations. Each person would provide 600 speech samples.

(600 samples/person x 400 persons/etiology x 5 etiologies = 1,200,000 samples)

Our schedule of research procedures is:

1. February or March-August 2023: data collection of speech samples from 400 people with Parkinson's. Parkinson's Disease is "etiology 1".
2. August 2023-August 2024: data collection of speech samples from 1,600 people with other etiologies to be determined (i.e., voted on by our Advisory Committee). One of these etiologies will be ALS. The other three etiologies are to be determined.

In Year 1, we focus on people with Parkinson's and therefore, recruitment will be managed by our partner the Davis Phinney Foundation, a well-known non-profit advocacy group for people with Parkinson's. DPF will distribute our recruitment flyer (see **Attachment 3, recruitment for speech**) and engage in informational sessions with potential participants. (In Year 2, we will do the same procedure for other populations of interest, such as ALS patients. Therefore, in Year 2, we will add additional patient advocacy organizations to assist in recruitment, such as Team Gleason to recruit patients with ALS.)

Data collection of speech samples in Year 1 will be a collaboration of UIUC and LSVT Global team members. Potential participants will be screened both with a questionnaire and by providing a short set of "quality control" speech samples (**Attachment 4**). If the participant does not pass screening, they will be thanked for their interest. Otherwise, the participant is eligible for the study and can do the informed consent process (**Attachment 5**) and then engage in contributing speech samples (**Attachment 7**).

Participants can do as many recordings as they wish at whatever time of day is convenient for them. Participants will be able to login to the system at any time, 24/7.

In Year 2, this procedure will be performed with patients from other etiologies with additional advocacy organizations as partners.

Participants also have the option to provide additional data about themselves, such as their age, race and ethnicity, year of their diagnosis, and other information as shown in **Attachment 9**. These "metadata tags" are completely optional but are helpful for analysis.

The collected speech samples will be stored securely in a custom database built by the UIUC Beckman Institute. All samples are stored with a unique participant ID code along with any of the optional

metadata tags. All samples are annotated by our UIUC research team with technical information about the acoustic waveform and other information.

The entire database of speech samples will be shared with our coalition partners (Amazon, Apple, Google, Meta, and Microsoft). Each partner has signed a data use agreement with UIUC that allows these deidentified data to be used for improvements in speech recognition technology and assures the privacy of participants and confidentiality of data. In the future, other partners may join this coalition, subject to a vote by the current members, and those future partners would also sign a data use agreement with the same terms and conditions.

Section 8. PERFORMANCE SITES TO INCLUDE INTERNATIONAL, SCHOOL, AND COLLABORATIVE STUDIES

8A. List all research sites for the protocol. For non-University of Illinois at Urbana-Champaign sites, describe their status of approval and provide contact information for the site. If the site has an IRB, note whether the IRB has approved the research or plans to defer review to the University of Illinois at Urbana-Champaign.

Performances Sites

#1 University of Illinois Urbana-Champaign

#2 Davis Phinney Foundation, Colorado

#3 LVST Global, Colorado and Arizona

If there are additional performance sites, include them on an attachment and check here:

8B. Is this a multi-center study in which the Illinois investigator is the lead investigator, or the University of Illinois at Urbana-Champaign is the lead site? Yes No

If yes, answer 8C and 8D. If no, proceed to Section 8E.

8C. Who is the prime recipient of funding, if funded? UIUC

8D. What is the management and communication plan for information that might be relevant to the protection of research subjects (e.g. unanticipated problems involving risks to subjects, interim results, and protocol modifications)? UIUC will issue subawards to DPF and LSVT Global. UIUC, DPF, and LSVT Global will establish a regular series of Zoom meetings with shared documents on Box or Teams. Any issues with participant engagement will be discussed regularly and remediated as appropriate. UIUC is responsible for monthly reports out to our founding partners, the Artificial Intelligence Accessibility Consortium.

8E. If subjects will be recruited from Illinois public or private elementary or secondary schools, additional deadlines and procedures may apply. Criminal background clearances might be required. Special consideration must be given to the exclusion of protected populations. Please contact the [School University Research Relations \([contact]\)](mailto:[contact]) for more information. Select one: Illinois schools will be used Illinois schools will not be used

Section 9. SUBJECT ENROLLMENT GOAL & EQUITABLE SELECTION OF SUBJECTS

9A. For each performance site, indicate the estimated total number of participants.

Performance Site	# Male	# Female	Total
#1 UIUC (20 for focus groups, 2000 for speech samples)	1010	1010	2020
#2 Davis Phinney Foundation collaborates with UIUC on recruitment	1000	1000	2000
#3 LVST Global collaborates with UIUC on focus groups, intake and collection of speech samples	1010	1010	2020
TOTALS	1010	1010	2020

If additional performance sites are included on an attachment, check here:

9B. Select all participant populations that will be recruited.

Age:

Adults (18+ years old)
 Minors (<17 years old)
 Specific age range, *please specify:*

Gender:

No targeted gender (both men and women will be recruited/included)
 Targeted gender, *please indicate:* Men/boys Women/girls Other, *please specify:*

Race/Ethnicity:

No targeted race or ethnicity (all races and ethnicities will be recruited/included)
 Targeted race or ethnicity, *please specify:*

College Students:

No targeted college population
 UIUC general student body
 Targeted UIUC student population, *provide the instructor or course information, name of the departmental subject pool, or other specific characteristics:*
 Students at institution(s) other than UIUC, *please specify:*

Any research with students on UIUC's campus needs to be registered with the [Office of the Dean of Students](#).

Other:

Inpatients
 Outpatients
 People who are illiterate or educationally disadvantaged
 People who are low-income or economically disadvantaged
 People with mental or cognitive disabilities or otherwise impaired decision-making capacities
 Adults with legal guardians
 People who are non-English speaking
 People with physical disabilities
 Pregnant or lactating women, human fetuses, and/or neonates

Prisoners or people with otherwise limited civil freedoms
 Other, *please specify*: Adults with caregivers to help participants use computers

9C. Describe additional safeguards included in the protocol to protect the rights and welfare of the populations selected above.

We have designed the remuneration plan to include support for caregivers.

Our subawards with DPF and LSVT Global are meant to provide extra support for potential participants. DPF's recruitment activities include providing information and support as needed to potential participants to answer their questions. If a potential participant does not seem able to provide informed consent, they will not be recruited. LSVT Global will provide an intake coordinator and a number of mentors to support data collection. We anticipate that many participants will need advice and support during their attempts at data collection online, and so they will be able to schedule time with an LSVT Global mentor to get help.

Section 10. INCLUSION/EXCLUSION

10A. List specific criteria for inclusion and exclusion of subjects in the study, including treatment and control groups.

For the main study to collect speech samples, total n=2000 where Cohort 1 (n=400) etiology is Parkinson's Disease, and Cohort 2 etiologies are still to be decided (n=1600) for Year 2.

Inclusion criteria:

- Adult (age \geq 18 years)
- Self-reported diagnosis of Parkinson's Disease or other etiology of interest
- Reads and speaks English
- Has a valid email address
- Ability to access web browser to participate in study

Exclusion criteria:

- Is a resident of the State of Washington, Texas, or Illinois (because these states have privacy laws that would not allow us to collect 'voice prints')
- If quality control screening of initial speech samples "fails" because of poor data quality (e.g., poor quality recording environment, or person's speech is "too typical" and not sufficiently interesting to continue collecting)

10B. Explain how the inclusion/exclusion criteria will be assessed and by whom. If special expertise is required to evaluate screening responses or data, list who will make this evaluation and describe their training and experience.

Assessing the inclusion/exclusion criteria will be in collaboration with patient advocacy organizations. In Year 1, that will be Davis Phinney Foundation and LSVT Global.

10C. Drafts or final copies of all screening materials are attached. Yes Not Applicable

10D. Describe procedures to assure equitable selection of subjects. Justify the use of the groups marked in Section 9B. Selection criteria that target one sex, race, or ethnic group require a clear scientific rationale.

We will offer participants the optional ability to provide demographic data, so that we can assess the diversity and equitable representation of our sample.

Section 11. RECRUITMENT

11A. Select all recruitment procedures that will be used.

- Student subject pool, *please specify*:
- Email distribution
- MTurk, Qualtrics Panel, or similar online population, *please specify*:
- US Mail
- Flyers/brochures
- Website ad, online announcement (e.g. eWeek), or other online recruitment, *please specify*: newsletter announcements via organizations that advocate for and support people with disabilities.
- Newspaper ad
- Verbal announcement
- Other, *please specify*:
- Not applicable (secondary data only)

11B. Drafts or final copies of all recruitment materials (including verbal scripts) are attached.

Yes Not Applicable

11C. For each group of participants, describe the details of the recruitment process.

In Year 1, Davis Phinney Foundation will include our recruitment flyer in their distribution channels, will also host optional information and Q&A sessions with potential participants, and will answer individual questions as needed from potential participants. The UIUC Speech Accessibility Project's website will remain as a public source of information, including an updated FAQ list that may be updated based on feedback from DPF.

Section 12. REMUNERATION AND PLAN FOR DISTRIBUTION

Refer to the University [Business and Financial Policies and Procedures](#) for further guidance on the compensation process and reporting requirements.

12A. Will subjects receive inducements or rewards before, during, or after participation?

Yes No

If yes, complete the rest of Section 12. If no, proceed to Section 13.

12B. Select all forms of remuneration that apply.

- Cash, *please specify amount*:

Check, please specify amount:
 Gift Certificate, please specify amount: Amazon ecodes adding up to \$180 per data contributor and up to \$90 per caregiver.
 Lottery, please specify amount: and odds:
 Course Credit, please specify amount: and specify equivalent alternative activity:
 Other, please specify:

12C. Will payment be prorated before, during, or after participation?

Yes, please specify how: prorated by number of recorded sentences uploaded to our system
 No

12D. For each group of participants, describe the details of the remuneration plan, including how, when and by whom they will be notified.

Our project plans to obtain a total of 600 recorded sentences per participant. Each participant will be compensated with up to \$180: \$60 after recording the 200th sentence, an additional \$60 after recording their 400th sentence, and an additional \$60 after recording their 600th sentence.

In addition to the participant compensation described above, participants will also be able to name a caregiver who is assisting them with performing the computer usage tasks in this study, and to specify additional compensation to the caregiver. Named caregivers will be compensated with up to \$90: \$30 after recording the 200th sentence, an additional \$30 after recording their 400th sentence, and an additional \$30 after recording their 600th sentence.

The NOVA H customized database system will track number of sentences per participant that are uploaded. The database will have a regular schedule of quality control checks and a built-in alert to remind the NOVA H project manager that payments are due as appropriate. The NOVA H project manager will then use the usual UIUC procedure to compensate the participants via automated email messages containing an appropriate Amazon ecode.

The Beckman Institute is fully aware of OBFS guidance on potential IRS tax implications of human subject payments. The NOVA H project manager will assure that the team follows OBFS guidance and will work closely with the Beckman business affairs office to ensure that tax implications are addressed.

12E. The information listed above is provided on the relevant consent forms.

Yes

Section 13. RISKS & BENEFITS

13A. Describe all known risks to the participants for the activities proposed, such as risks to the participants' physical well-being, privacy, dignity, self-respect, psyche, emotions, reputation, employability, and criminal and legal status. Risks must be described on consent forms.

Risks include (1) the risk of loss of privacy in case any research institution that has been granted data access violates their data use agreement by releasing participant speech samples to people not covered by the agreement, and (2) the risk that subjects may get tired while recording sentences.

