16D. Describe provisions to protect the privacy interests of subjects. Separation of identifiable information from speech samples in the database. Participant's recorded speech samples are stored on a virtual machine that contains no other information contributed by the participant; on this virtual machine, the participant's identity is coded using a participant code that consists of a randomly generated sequence of letters and numbers. Participant contact information, and any other information contributed by the participant, are stored in a separate database, on a separate virtual machine, accessible only by University of Illinois employees with administrative access to the server. Both virtual machines are implemented on the Beckman Institute Dell EMC Isilon/PowerScale encrypted storage array. The Isilon system currently has storage to accommodate approximately 1 PB of data, with over 300 TB of open space available. We can add additional storage, up to a maximum of 64 PB, by adding additional nodes to the array. The primary system is in a secure server room in the Beckman Institute building, and the disaster recovery (DR) system is in a secure data center on the Illinois State University campus. Both systems are fully encrypted and connected on the University of Illinois WAN. The data is synchronized from the production site to the DR site 3 times a day. Snapshots of the data are taken 3 times a day, and each is retained for 4 weeks. In addition, a monthly snapshot is taken and retained for 12 months. Participant speech data, and text transcripts created by University of Illinois annotators, will be distributed to coalition partners approximately once per month during the period of data collection and annotation. Each data distribution will consist of a single archive file, compressed and encrypted using a secure key technology such as RSA or DSA, so that it can only be decompressed by individual researchers who have been authorized by the coalition partner company under the terms of the data use agreement. Data distributions to coalition partners will never contain any information contributed by a participant other than their recorded speech samples.

16E. Describe the training and experience of all persons who will collect or have access to the data. The team members are up to date on CITI modules and Research IT trainings on data privacy and security.

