5.3 The terms and conditions of the Agreement (including but not limited to Sections 11, 13.d., and 13.f. of the Agreement) shall continue to apply with respect to Data User's exercise of its license rights pursuant to Section 9.b and this Exhibit C; provided, however, in the event of a conflict between the terms and conditions of this Exhibit C and the terms and conditions elsewhere in the Agreement, the terms and conditions of this Exhibit C shall prevail.

5.4 Any notices provided under this Exhibit C shall be provided pursuant to Section 13.e. of the Agreement using the applicable party contact information listed in the Agreement.

6. Definitions

6.1 "Data" means the Licensed Speech Signal Data (as defined in the Agreement) that Data User receives under the Agreement during the Term while such Data User is a party to the Agreement, in modified or unmodified form. Data does not include Results.

6.2 "Permitted Purpose" means research by or on behalf of Data User to advance understanding of machine learning-related data variances associated with atypical speech variations, and the development of products, technologies, and services by or on behalf of Data User to improve communications and increase access to technology, including computational use, processing of Biometric Data, and the creation and training of machine learning solutions and artificial intelligence models including for research and for commercial purposes.

6.3 "Result" means anything that Data User develops or improves for the Permitted Purpose that does not include more than a de minimis portion of the Data (e.g., summary statistics such as the number of speakers, and the gender, age range, etiology, ethnicity, and similar characteristics of speakers) on which the use is based. Results may include de minimis portions of the Data necessary to report on or explain use that has been conducted with the Data, such as figures in scientific papers, but do not include more. For example, machine learning and artificial intelligence models trained on Data (and which do not include more than a

de minimis portion of Data) are Results to the extent they are developed by or on behalf of Data User pursuant to the terms of the Agreement and this Exhibit C.

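### Does monthly release of all study speech, with no common speaker-level training/test split, undermine the study?

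*Combined protocol and SAP*

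**What the plan says.** The aim in Sections 6A and 7F is to assemble, annotate and share a speech corpus: 2,000 people, five etiologies, 600 samples each. The provisions that bear on this point are:

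- **Scope of sharing (7F).** "The entire database of speech samples will be shared with our coalition partners (Amazon, Apple, Google, Meta, and Microsoft". Later entrants are foreseen: "In the future, other partners may join this coalition, subject to a vote by the current members".
- **Timing (16D).** Speech and transcripts "will be distributed to coalition partners approximately once per month during the period of data collection and annotation".
- **Content (16D).** "Data distributions to coalition partners will never contain any information contributed by a participant other than their recorded speech samples".
- **Speaker code (7F, 16D).** "All samples are stored with a unique participant ID code", and on the speech server the "identity is coded using a participant code that consists of a randomly generated sequence of letters and numbers". Section 16D does not say whether the code travels with a release.
- **Permitted use (data use terms, clause 6.2).** This includes "the creation and training of machine learning solutions and artificial intelligence models including for research and for commercial purposes".
- **Schedule (7F).** The first etiology is Parkinson's: "February or March-August 2023: data collection of speech samples from 400 people".
- **Benefit (13E, 13F).** Recognisers that are more accurate on disordered speech are listed as a potential benefit to society. No metric, test set or comparison is attached.

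Clause 6.1 defines the released data by reference to a term in the main membership agreement. Section 4D says that agreement is attached to the application, but its body is not in the available file, and the data use terms there begin at clause 2.1.

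**The concern.** Anyone who has built a speech-recognition benchmark will look for a speaker-level hold-out and find none here. A model trained on a speaker's recordings usually does better on that speaker's other recordings, so an honest accuracy figure needs speakers the model has not met. Here every partner receives everything, month by month, and may train on it. Partners could split by recording, or split by speaker in different ways, and a partner that joins later would find no standard split to adopt.

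The step also looks irreversible: once a model has been trained on a speaker, that speaker is no longer unseen for it. The Parkinson's cohort is scheduled for collection by August 2023, so a rule introduced only in Year 2 might come too late for it. If the project's case rested on showing that accuracy improved across partners, the lack of a common test set would weaken that showing.

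A smaller question sits alongside. Clause 6.3 allows results to report speaker characteristics such as etiology, while 16D, Attachment 4 and Attachment 9 keep participant-supplied information from partners.

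**Working it through.** **1. The plan's own figure.** From 7F: 600 samples × 400 people × 5 etiologies = 1,200,000, and 400 + 1,600 = 2,000 people. Both reproduce. This is a collection target; no alpha, power, effect size or accuracy margin is attached to it.

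**2. Share at stake in Year 1.** 400 × 600 = 240,000 samples; 240,000 / 1,200,000 = 20%. The schedule dates collection. Releases include transcripts and run through annotation, so collection by August 2023 does not establish release by then, and release is not the same as use in training.

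**3. Splitting by recording (assumed 10%).** 600 × 0.1 = 60 test and 540 training recordings per speaker, so practically no test speaker would be unseen.

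**4. Five partners splitting by speaker independently.** The documents give no hold-out fraction, so h is assumed. Expected speakers out of 2,000:

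| h | In both test sets of a given pair, 2000h² | In at least two of five, 2000[1 − (1−h)⁵ − 5h(1−h)⁴] | In all five, 2000h⁵ |
|---|---|---|---|
| 5% | 5 | 45 | 0.0006 |
| 10% | 20 | 163 | 0.02 |
| 20% | 80 | 525 | 0.64 |

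A single common split at 10% gives 2000 × 0.1 = 200 speakers, or 400 × 0.1 = 40 per etiology. Without stratification, the test speakers in one etiology follow a hypergeometric(2000, 400, 200) distribution: mean 40, SD 5.4, 95% range 30 to 51.

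**5. Does any planned output use these numbers?** This step decides the point.

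- The deliverable (6A, 7F) is the corpus. Its size and content do not depend on how partners later divide it.
- No endpoint, hypothesis or analysis of recognition accuracy appears in the available text, so no estimate can be biased by training and test speakers overlapping.
- Section 13E names a potential benefit. A partner can build a better recogniser, and show it on its own held-out speakers, without sharing a test set with four others.
- Section 13F weighs that benefit against minimal risk and relies on no benchmark.

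**6. Are partners prevented from splitting by speaker?** Nothing available prevents it. Section 16D excludes information contributed by the participant, and the code is generated by the university. Clause 4.1(i) allows pseudonymized data, and clause 6.3 contemplates reporting a count of speakers. Neither clause proves that the code is released, but both are compatible with it.

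**7. The labelling question.** Clause 6.3 describes what results may contain. It does not oblige the university to release etiology or demographic labels, so it does not contradict 16D, Attachment 4 or Attachment 9.

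**The case for a change.** The strongest argument for the concern is cost and timing. Only the university is certain to hold a speaker code for every sample. A random label assigned at consent would take one field, would leave enrolment and the release schedule alone, and would respect 16D because the participant does not contribute it. Delay uses up unseen speakers.

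Much of this stands. The text is silent on a split, the arithmetic is right, and a standard partition would make the corpus more useful. It is also true that 16D leaves unsaid whether the code and an etiology label accompany a release; a sentence on each would help the reader.

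It does not turn the silence into an error, and the benefit of a label is less secure than it looks:

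- A label could only ask partners not to train on test speakers, because clause 6.2 licenses training and the partners have already signed. The set would be common but not protected.
- At an assumed 80/10/10, compliance would remove 200 + 200 = 400 speakers from training, or 400 × 600 = 240,000 samples. That equals one whole etiology.
- Stratifying by etiology needs a recorded diagnosis. In the available materials the only such item is question 2 of the pre-screening questionnaire (Attachment 4), and participants are told those answers serve only to confirm eligibility. Cohort membership might substitute in Year 1, but Year 2 covers four etiologies.
- Assignment at consent would not guarantee 40 complete test speakers per etiology. Payment at 200, 400 and 600 sentences (12D) anticipates partial contribution, and clause 4.1(iv) provides for deletion after withdrawal.

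**Conclusion.** The concern does not hold. Carried out exactly as written, the plan yields the database it promises, and no conclusion it intends to draw depends on a common set of unseen speakers. The effect on the study's own results is nil. The contrast between 0.02 and 200 common test speakers is correct for its assumptions: a 10% hold-out, five partners and independent splits. Independence is pessimistic for members of a coalition, who could agree a split among themselves, and none of these assumptions comes from the documents.

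Two conditions apply. First, the judgement rests on there being no accuracy endpoint or partner comparison in the available text; if one were added, a speaker-level hold-out would become a real design requirement. Second, release content is tied to a membership agreement whose body is not in the file, so the lack of a partition cannot be charged to the plan as a whole. What remains is a reasonable preference about corpus design and an optional clarification of what labels a release carries.
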